3.0 STUDY DESIGN

3.1 DESCRIPTION OF STUDY

This clinical trial is a Phase 2, multicenter, open-label study in subjects with histologically documented MCL who have relapsed after, or were refractory to, \geq 1 (but not $>$ 5) prior

treatment regimens. Subjects will be enrolled and will take 100 mg of acalabrutinib BID in repeated 28-day cycles.

Treatment with acalabrutinib may be continued until disease progression or unacceptable drug-related toxicity, whichever occurs first. Dose modification provisions are outlined in [Section 3.5.6](#). Note: Temporary withholding of study drug for as little as 7 days can cause a transient worsening of disease and/or of constitutional symptoms. Refer to [Section 3.8](#) for more information on assessing disease progression under these circumstances. An early termination visit is required for any subjects who permanently discontinue study drug for any reason (except for death, lost to follow up or withdrawal of consent), including disease progression. In addition to the early termination visit, all subjects who discontinue study drug will have a safety follow-up visit 30 (+ 7) days after his or her last dose of study drug.

All subjects will have hematology, chemistry, and urinalysis safety panels done at screening. Once dosing commences (Day 1), all subjects will be evaluated for safety, including serum chemistry and hematology once weekly for the first 4 weeks, every 2 weeks in Cycle 2, every 4 weeks in Cycles 3 to 12, and every 24 weeks thereafter. Tumor assessments will be performed at 8- to 24-week intervals throughout the study.

This study will enroll approximately 117 subjects.

Refer to [Appendix 4](#) for a comprehensive list of study assessments and their timing. The end of study is defined as the last subject last visit date.

The primary efficacy analyses will be based on investigator assessment. An Independent Review Committee (IRC) will assess the efficacy endpoints in accordance with the IRC charter provided separately from this document.

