3.4.2 Exclusion Criteria

Subjects will be ineligible for this study if they meet **any** of the following criteria:

1. Prior malignancy, except for adequately treated basal cell or squamous cell skin cancer, in situ cervical cancer, or other cancer from which the subject has been disease free for ≥ 2 years or which will not limit survival to < 2 years. Note: these cases must be discussed with the medical monitor.
2. A life-threatening illness, medical condition, or organ system dysfunction which, in the investigator's opinion, could compromise the subject's safety, interfere with the absorption or metabolism of acalabrutinib, or put the study outcomes at undue risk.
3. Significant cardiovascular disease such as uncontrolled or symptomatic arrhythmias, congestive heart failure, or myocardial infarction within 6 months of screening, or any Class 3 or 4 cardiac disease as defined by the New York Heart Association Functional Classification, or corrected QT interval (QTc) > 480 msec.
4. Malabsorption syndrome, disease significantly affecting gastrointestinal function, or resection of the stomach or small bowel, gastric bypass, symptomatic inflammatory bowel disease, or partial or complete bowel obstruction.
5. Any immunotherapy within 4 weeks of first dose of study drug.
6. The time from the last dose of the most recent chemotherapy or experimental therapy to the first dose of study drug is < 5 times the half-life of the previously administered agent(s).
7. Prior exposure to a BCR inhibitor (eg, BTK, phosphoinositide-3 kinase [PI3K], or SYK inhibitors) or BCL-2 inhibitor (eg, ABT-199).
8. Ongoing immunosuppressive therapy, including systemic or enteric corticosteroids for treatment of MCL or other conditions. Note: Subjects may use topical or inhaled corticosteroids or low-dose steroids (≤ 10 mg of prednisone or equivalent per day) as therapy for comorbid conditions. During study participation, subjects may also receive systemic or enteric corticosteroids as needed for treatment-emergent comorbid conditions.
9. Grade ≥ 2 toxicity (other than alopecia) continuing from prior anticancer therapy including radiation.
10. Known history of human immunodeficiency virus (HIV) or active infection with hepatitis C virus (HCV) or hepatitis B virus (HBV) or any uncontrolled active systemic infection.

11. Major surgery within 4 weeks before first dose of study drug.
12. Uncontrolled autoimmune hemolytic anemia or idiopathic thrombocytopenia purpura.

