3.7 PRECAUTIONS

3.7.1 Risks Associated with Acalabrutinib Treatment

The following summarizes the experience with acalabrutinib in hematological cancer studies. Full details regarding the clinical safety of acalabrutinib are presented in Sections 5 and 6 of the Acalabrutinib IB.

Hemorrhage

Bleeding events, some fatal, including central nervous system, respiratory, and gastrointestinal hemorrhage, have been reported in patients treated with acalabrutinib.

Patients receiving antiplatelet or anticoagulant therapies may be at increased risk of hemorrhage and should be monitored for signs of bleeding. As a precaution, it is suggested per protocol that acalabrutinib be withheld for at least 3 days pre- and post-surgery.

Patients with hemorrhage should be managed per institutional guidelines or as clinically indicated.

Infections

Serious infections, including fatal events, have been reported in patients treated with acalabrutinib. Consider prophylaxis in subjects who are at increased risk for opportunistic infections. Patients should be monitored for signs and symptoms of infection and treated as medically appropriate. Refer to the sections below for additional information and monitoring guidance for viral hepatitis and additional information and management guidance for signs and symptoms of progressive multifocal leukoencephalopathy (PML).

Hepatitis B Virus Reactivation

Cases of hepatitis B virus (HBV) reactivation have been reported in patients treated with acalabrutinib with 1 case resulting in liver failure and death. Subjects who are anti-HBc positive or have a known history of hepatitis B virus (HBV) infection should be monitored every 3 months with a quantitative PCR test for HBV DNA. Monitoring for HBV **in these subjects** should continue until 12 months after last dose of acalabrutinib. Any subject with a rising viral load (above lower limit of detection) should discontinue study drug and have antiviral therapy instituted and a consultation with a physician with expertise in managing hepatitis B. Insufficient data exist regarding the safety of resuming acalabrutinib in subjects who develop HBV reactivation.

Progressive Multifocal Leukoencephalopathy

Cases of PML have been reported in patients treated with acalabrutinib. Signs and symptoms of PML may include cognitive and behavioral changes, language disturbances, visual disturbances, sensory deficits, weakness, and coordination and gait difficulties.

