4.1.2 Medical History

Collect and record the subject's complete history through review of medical records and by interview. Concurrent medical signs and symptoms must be documented to establish

baseline severities. A disease history, including the date of initial diagnosis and list of all prior anticancer treatments, and responses and duration of responses to these treatments, will also be recorded.

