Abbreviations: AE = adverse event; ALT = alanine aminotransferase; AST = aspartate aminotransferase; BUN = blood urea nitrogen; CR = complete remission; CT = computed tomography; DFU = discontinuation follow-up; ECG = electrocardiogram; ECOG = Eastern Cooperative Oncology Group; ET = early termination; HBV = hepatitis B virus; Ig = immunoglobulin; LDH = lactate dehydrogenase; LTFU = long-term follow-up; mos = months; MRD = minimal residual disease; PCR = polymerase chain reaction; PD = pharmacodynamic; PE = physical exam; PET = positron-emission tomography; PK = pharmacokinetic; CCI [REDACTED] Q3M = every 3 months; SAE = serious adverse event.

Footnotes for ACE-LY-004 Schedule of Study Activities:

- Screening tests should be performed within 21 days before the first administration of study drug, unless otherwise indicated.
- Treatment with acalabrutinib may be continued until disease progression or unacceptable drug-related toxicity, whichever occurs first. After Cycle 24, subjects will continue to have scheduled visits every 24 weeks as outlined on the schedule of assessments.
- An early termination visit will be done for subjects who permanently discontinue study drug early for any reason (except for death, lost to follow up or withdrawal of consent). In addition, a 30-day (+ 7 days) safety follow-up visit is required for **all** subjects after his or her last dose of study drug to monitor for AEs, regardless of whether the subject receives a new anticancer therapy or demonstrates disease progression within this timeframe.
- The screening physical examination will include, at a minimum, the general appearance of the subject, height (screening only) and weight, and examination of the skin, eyes, ears, nose, throat, lungs, heart, abdomen, extremities, musculoskeletal system, lymphatic system, and nervous system. Symptom-directed physical exams, including tumor assessments by palpation and attention to neurologic signs and symptoms of progressive multifocal leukoencephalopathy, are done thereafter.
- Vital signs (blood pressure, heart rate, and temperature) will be assessed after the subject has rested in the sitting position.
- Subjects should be in supine position and resting for ≥ 10 minutes before study-related ECGs.

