- q. A pretreatment computed tomography (CT) scan with contrast (unless contraindicated) is required of the chest, abdomen, and pelvis and any other disease sites (eg, neck) within 30 days before the first dose of study drug. A pretreatment positron-emission tomography (PET)/CT scan within 60 days from first dose of study drug is also required. During treatment, CT scans with contrast (unless contraindicated) will be performed for tumor assessments at the end of Cycle 2 (± 7 days), Cycle 4 (± 7 days), and Cycle 6; and then every 6 cycles (24 weeks) thereafter, or more frequently at the investigator's discretion. For Cycles ≥ 6 , CT and PET/CT scans may be performed within an imaging window of up to 21 days before and up to 7 days after the scheduled study visit date. During treatment, PET/CT scans will be performed at the end of Cycle 2 (± 7 days) and Cycle 6 as well as any time to confirm CR or as clinically indicated. Subjects with confirmed CR are not required to undergo further PET/CT scans on study unless there is suspicion of progressive disease. Endoscopy is mandatory to confirm CR for any subjects with a documented history of gastrointestinal involvement.
- r. Subjects who discontinue will be followed approximately every 24 weeks from the date of last dose until study exit to assess survival and the use of alternative anticancer therapy. During this period, CT scans will be done approximately every 24 weeks until disease progression or until the start of alternative anticancer therapy.
- s. Subjects who progress or start alternative anticancer therapy will be followed approximately every 24 weeks until study exit to assess survival and the use of alternative anticancer therapy.
- t. The indicated samples at this timepoint (Cycle 1 Day 1) must be drawn predose.
- u. **CCI**
- v. Subjects who are hepatitis B core antibody positive (or have a known history of HBV infection) should be monitored Q3M with a quantitative PCR test for HBV DNA. HBV monitoring should last until 12 months after last dose of study drug. Any subject with a rising viral load (above lower limit of detection) should discontinue study drug and have antiviral therapy instituted and a consultation with a physician with expertise in managing hepatitis B.

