- If there is a significant change, follow the process described in “Potential Hy’s Law Criteria Met” in this Appendix for reporting PHL as an SAE.

LABORATORY TESTS

The list below represents a comprehensive list of follow-up tests that may aid in assessing PHL/HL.

Test results used to assess PHL/HL should be recorded on the appropriate eCRF.

Additional standard chemistry and coagulation tests	GGT LDH Prothrombin time INR
Viral hepatitis	IgM anti-HAV IgM and IgG anti-HBc HBsAg HBV DNA IgM and IgG anti-HCV HCV RNA IgM anti-HEV HEV RNA
Other viral infections	IgM & IgG anti-CMV IgM & IgG anti-HSV IgM & IgG anti-EBV
Alcoholic hepatitis	Carbohydrate deficient transferrin (CD-transferrin)
Autoimmune hepatitis	Antinuclear antibody (ANA) Anti-Liver/Kidney Microsomal Ab (Anti-LKM) Anti-Smooth Muscle Ab (ASMA)
Metabolic diseases	alpha-1-antitrypsin Ceruleplasmin Iron Ferritin Transferrin Transferrin saturation

Reference

FDA Guidance for Industry (issued July 2009). Drug-induced liver injury: Premarketing clinical evaluation
<http://www.fda.gov/downloads/Drugs/GuidanceComplianceRegulatoryInformation/Guidances/UCM174090.pdf>

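### Anti-HBc positivity triggers HBV DNA monitoring every 3 months, but the supplied protocol version schedules no assessment that establishes anti-HBc status

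*Protocol*

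**What the plan says.** Protocol 3.7.1 names hepatitis B reactivation as a risk of acalabrutinib, "with 1 case resulting in liver failure and death". It requires HBV DNA testing every 3 months, until 12 months after last dose, in subjects who are anti-HBc positive or have a known HBV history. Footnote v of Appendix 4 repeats the trigger: "Subjects who are hepatitis B core antibody positive (or have a known history of HBV infection) should be monitored Q3M". The action rule is: "Any subject with a rising viral load (above lower limit of detection) should discontinue study drug". Antiviral therapy and a specialist consultation follow.

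On finding these subjects, Protocol 3.1 says: "All subjects will have hematology, chemistry, and urinalysis safety panels done at screening". Protocol 4.1.2 adds a "complete history through review of medical records and by interview". Exclusion criterion 10 (3.4.2) bars active HBV infection and names no test. Anti-HBc is listed as a test in one place, the laboratory table of Appendix 5, which is described as a "comprehensive list of follow-up tests that may aid in assessing PHL/HL" (PHL/HL meaning potential or actual Hy's law cases).

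**The concern.** The monitoring rule has two entry routes, and only one has a procedure behind it. A known HBV history can come from the records and interview. Anti-HBc status needs a blood test, and none is scheduled. Other criteria that rest on a measurement do have one: the QTc limit in exclusion 3 has a screening ECG, and the count limits in exclusion 17 have screening hematology.

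What is at stake is a safety rule that may not reach some of the people it was written for. A subject who is anti-HBc positive with no recorded history need not be identified, so HBV DNA is never scheduled and the stop rule has no value to act on. The protocol itself reports a fatal case.

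**Working it through.** No figure in the plan needs reproducing. The check is a search for any scheduled step that could establish anti-HBc status, followed by simple arithmetic on schedules.

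**1. Where anti-HBc status could come from**

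- Protocol 3.1, screening panels: hematology, chemistry, urinalysis. No serology.
- 4.1.13, serum chemistry: 20 analytes, none a hepatitis marker.
- 4.1.12 and 4.1.14 to 4.1.16 (blood count, urinalysis, lymphocyte subsets, immunoglobulins): no HBV marker.
- 4.1.17, HBV testing: PCR only, in subjects already selected.
- Appendix 4, laboratory block: an HBV PCR row, but no serology row.
- 3.4.2, criterion 10: excludes active infection, with no test named.
- 4.1.2, medical history: finds a known history. It finds anti-HBc positivity only if a result is already in the records.
- Appendix 5: lists anti-HBc for the work-up of a potential Hy's law case (AST or ALT at least 3 × ULN with bilirubin at least 2 × ULN), when liver injury is already evident.

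Scheduled anti-HBc tests at screening or baseline: 0.

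**2. What identification changes**

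Every 3 months is 365.25 / 4 = 91.3 days, so an identified subject has about 365.25 / 91.3 = 4 HBV DNA tests a year. An unidentified subject has 0.

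**3. What else would be seen**

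ALT, AST and bilirubin are scheduled for everyone: weekly in the first 4 weeks, every 2 weeks in Cycle 2 and every 4 weeks in Cycles 3 to 12. Section 3.1 then moves directly to every 24 weeks, while Appendix 4 keeps visits at Cycles 15, 18 and 21. From Cycle 24 the two agree: "After Cycle 24, subjects will continue to have scheduled visits every 24 weeks as outlined on the schedule of assessments". That is 24 × 7 = 168 days between panels. Chemistry reacts to liver injury rather than to viral load, so its cover is partial and later.

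**4. Which phase applies now**

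Protocol 1.5.2 reports 124 treated subjects with data through 01 June 2016, against about 117 planned, so enrollment appears complete. Cycle 24 ends at day 24 × 28 = 672. For a first dose on or before 01 June 2016, that is early April 2018 at the latest. Appendix 6 dates this version to the COVID-19 pandemic. Any of these subjects still on drug is therefore on the 24-week schedule.

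**5. How many subjects**

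Number affected = 124 × (share on drug or within 12 months of last dose) × (share with no anti-HBc result on record) × (share anti-HBc positive without a recorded history). The documents give none of the three shares. Purely as an assumption, take the last share as 1% to 10% and set the first two to 1. The result is 124 × 0.01 = 1.2 to 124 × 0.10 = 12.4 subjects. That is a ceiling under the assumption. The true number is lower to the extent that subjects have left follow-up or were tested before, and it may be zero.

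**The case against.** The strongest reply is that the screening that matters took place under documents we do not have. The 124 subjects were treated by 01 June 2016. The SAP is written to Amendment 6, dated 19 July 2016, and the supplied protocol is version 10. Earlier versions may have called for serology, or sites may have run it to confirm criterion 10. SAP 10.7.3.2 plans a listing of everyone with a hepatitis B test, so such results are captured, although that does not show that they include anti-HBc. Protocol 4.0 also allows extra laboratory work when clinically indicated. All of this stands. A reader might infer that enrolled subjects were never tested; the documents do not support that. They show only that this version does not require a test. The reply limits the size of the problem but does not close the gap, because a trigger should not depend on unstated practice.

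A second reply is liver chemistry. It is frequent through Cycle 12, and the Appendix 5 list includes HBV DNA and anti-HBc. This is real cover and should be credited. It is thinner after Cycle 24, where remaining subjects now are.

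A third is redaction: Section 4.1.8, footnote u and one Appendix 4 row are blacked out. The redacted row lies outside the laboratory block, and HBV testing has its own visible section and row, so a hidden serology test is unlikely.

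A reader might also go further and argue that the stop rule fails for want of a baseline, since the first mark in the HBV PCR row falls at Cycle 3 Day 28 (3 × 28 = day 84). The documents do not bear that out. The rule can be read to act on a first detectable value, a first test at about 3 months fits the stated interval, and no endpoint or protocol action is shown to depend on separating entry infection from reactivation.

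Nor is the SAP's monthly, history-only wording an error, since it follows an older amendment.

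**Conclusion.** The concern holds in a limited form. In the supplied protocol version, anti-HBc positivity starts HBV DNA monitoring, but no scheduled assessment establishes it. An anti-HBc-positive subject without a recorded HBV history need not be identified or monitored. This is more than a missing detail, because a fully compliant site can miss a subject whom the rule is meant to protect, from a named risk with a fatal case.

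For such a subject the loss is about four HBV DNA tests a year, with liver chemistry as the remaining, later signal. The number of such subjects is unknown. The conclusion assumes that the redacted passages hide no serology test. It makes no claim about what was done at screening under earlier versions.

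**What to change.** Add to Protocol 3.7.1 and to footnote v of Appendix 4:

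*Subjects on study drug, or within 12 months of last dose, whose anti-HBc status is not on record will have anti-HBc tested once at the next scheduled blood draw (local laboratory acceptable). If positive, HBV DNA is tested at that time and then Q3M.*

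For any new enrollee, test anti-HBc at screening, with HBV DNA before first dose if it is positive or there is a known HBV history.

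The one-time test is best done before database closure, after which subjects who stay in this protocol have standard-of-care visits and only SAEs are collected (3.1).

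The cost is one serology test per subject of unknown status, one HBV DNA test at that time in any positive subject followed by the Q3M tests already prescribed, and an occasional local draw for subjects followed by telephone. Local laboratories already do the HBV PCR (4.1.17). The 3-month interval and the stop rule do not change, and subjects with a result on record need nothing more.

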Appendix 6. Management of Study Procedures During Pandemic

This appendix consolidates guidance for subject safety and ongoing access to medical care and investigational product during the global COVID-19 pandemic. The measures detailed below will be implemented across Acerta Pharma studies on a temporary basis until the pandemic is considered resolved by governmental and public health organizations, as applicable.

Regardless of the guidance below, please consider public health advice in your local market and individual risk/benefit in treatment decisions for subjects at your study site during the pandemic. Please also consider logistical requirements such as the ability of subjects to travel to the study site, accessibility of public transport, etc.

If the subject is unable or unwilling to visit the study site due to COVID-19 related reasons, investigators may ask enrolled subjects to use healthcare facilities local to the subject to ensure safety and efficacy measures are done per protocol. If a study assessment is not done at either the site or a facility local to the subject, then its absence should be documented as a protocol deviation. Any protocol deviations resulting from the COVID-19 situation should be recorded and prefixed with COVID-19.

Study Subject Participation

Conduct of Telephone Visits

Due to the current pandemic, it is conceivable that not all subject visit commitments may be able to be fulfilled. If a subject is unable or unwilling to attend a study visit, adaptation of the onsite visit to a telephone visit is recommended to ensure continuity of study care (as an interim measure; eg, telephone contacts instead of visits, shipping study medication to the subject). Priority should be given to maintaining ongoing safety follow-up (even if this is conducted by telephone contacts). Study sites should speak with their site monitor before performing a telephone visit so he or she may provide guidance regarding logistics that may need consideration. Also, study sites should speak with the site monitor if the subject cannot attend more than one onsite visit in succession, because multiple incomplete visits may have the potential to impact evaluation of study endpoints.

Acalabrutinib Dose Modification Recommendation for COVID-19

The sponsor recognizes that coronavirus 2019-nCoV (COVID-19) presents an increased risk for all subjects. Due to the potential impact of COVID-19 on multiple organ systems, the sponsor recommends the following dose modification and management plan for

subjects with confirmed or suspected COVID-19 while receiving treatment with acalabrutinib.

First and foremost, the following safety reporting guidelines are required:

All confirmed or suspected COVID-19-related adverse events (AEs) must be recorded in the eCRF. All dose modifications should be based on the worst Common Terminology Criteria for Adverse Events (CTCAE) grade. All interruptions or modifications must be recorded on the AE and drug administration eCRFs. The CTCAE general grading criteria should be used to evaluate COVID-19.

If an event is suspected to be COVID -19 infection, the sponsor recommends interrupting acalabrutinib and testing for COVID-19 per local guidance.

- If COVID-19 is ruled out, standard clinical practice and the study protocol procedures should be followed regarding any dose modifications required for management of severe infections.
- If COVID-19 is confirmed or diagnosis is suspected after evaluation, COVID-19 infection should be managed per local guidance until the subject achieves full recovery, defined as no signs or symptoms.

In case of COVID-19 positivity, the investigator must determine the risk and benefit of interruption versus continuation of acalabrutinib and whether to resume it at full or modified doses or discontinue treatment.

Please contact the study medical monitor for further discussion.

Comparator Drugs or Drugs Used in Combination with Acalabrutinib:

- Please refer to guidance from the manufacturer.

Drug-drug interactions (DDI) may occur with some of the drugs being used as best supportive care (eg, drugs that are strong inducers or inhibitors of cytochrome P450 [CYP]3A). Guidance is provided below:

Drug-Drug Interaction Guidance for Investigators with Subjects Enrolled in an Acalabrutinib Clinical Study who are COVID-19 Positive:

- The potential combination with chloroquine or 8-OH-chloroquine (8-OH-CHQ) and azithromycin are not predicted to have a pharmacokinetic DDI with acalabrutinib. However, both agents are known to cause cardiovascular risk of QT-prolongation. Therefore, the benefit-risk of initiating 8-OH-CHQ + azithromycin should be discussed with the medical monitor.

- Many antivirals and antibiotics are considered strong CYP3A4 inhibitors or inducers and are therefore likely to cause complex DDIs with acalabrutinib. The risk-benefit balance of acalabrutinib use in the setting of COVID-19 treatment should be discussed between the investigator and the medical monitor.
- Remdesivir is rapidly metabolized to a pharmacologically active metabolite, GS-443902. Based on published and publicly available data, remdesivir does not appear to inhibit CYP isoforms and will likely not interact in a meaningful way with drug transport systems. Remdesivir does not prolong QTc interval.
- Systemic steroids and acalabrutinib may impair the ability of the body to fight infection; it is best to avoid high-dose systemic steroids while taking acalabrutinib.
- The study protocol and investigator brochure should be referenced for other DDI information.

COVID-19 Specific Data Entry Instructions for Investigational Sites

Adverse Event Recording:

Currently no changes to normal data capture procedures are required for COVID-19 data in the eCRF. For subjects who have confirmed or who are suspected of having coronavirus infection, the infection should be documented as an AE or serious adverse event (SAE), in line with instructions for safety reporting documented in the clinical study protocol. Either “**COVID-19 Confirmed**” or “**COVID-19 Suspected**” should be used when reporting the event as follows:

- If test is positive, “COVID-19 confirmed” should be recorded in the AE field.
- If test is negative, AE/SAE signs and symptoms and/or other diagnosis should be recorded in the AE field(s).
- If test is not available and signs and symptoms, as judged by the investigator, are highly suspicious of COVID-19 infection, record “COVID-19 suspected” in the AE field.

Details of any testing or procedure to determine the status of COVID-19 infection should be documented on the Concomitant Procedure Form if available or on the appropriate eCRF page in the study.

For fatal SAEs, the Death Information Form, End of Study Treatment Form, and Study Exit Form should be completed.

Study Treatment Recording:

If an AE or SAE is associated with COVID-19, the investigator should determine whether the subject’s treatment with investigational product should continue, be interrupted, or be discontinued in accordance with the clinical study protocol.

For **dosing interruptions**, where applicable, the following guidelines should be used:

- Related to AE:
On the Dose Administration Forms(s), dose change/missed should be indicated with AE as the reason. The dosing stop date must correlate to the AE/SAE start/stop dates.
- Related to Logistics:
For subjects who have missed a study treatment due to an inability to travel to the clinic or for some other logistical reason, on the Dose Administration Form(s) dose change/missed should be indicated with Other as the reason, and “Logistic” as Other, Specify.

If these options are not available in the eCRF, then either dose discontinuation should be recorded (if permanently stopped) or a protocol deviation should be recorded, prefixed COVID19.

For **dosing discontinuations**, where applicable, the dosing discontinuation guidelines should be followed, and the End of Treatment Form(s) completed.

Capturing telephone contacts with subjects:

If a telephone visit is substituted for an onsite study visit, the following are guidelines for data capture:

1. If the visit is specified as a phone visit as per protocol, no additional action is required.
2. If the visit is listed as on-site but the subject will be contacted by phone, data should be completed as per a normal visit (ie, using the relevant eCRF pages to capture a phone Visit Date, and any possible assessment that can be obtained remotely should be captured, such as AEs, study drug administration and/or concomitant medications, and any additional safety information). All assessments that cannot be performed should be marked as not done or eCRF inactivated/blank. A protocol deviation should be recorded in the clinic notes prefixed COVID19 detailing the use of a phone visit in place of an onsite visit.
3. If the visit requires procedures that cannot be performed via telephone contact (eg, MRI or CT Scan), this should be discussed with the site monitor because this procedure may impact primary efficacy or safety analyses.

Acalabrutinib Site-to-Subject Drug Shipment Instructions During Pandemic Containment or in Case of Force Majeure

If a subject is definitively unable to physically go to the study site or unable to be represented by a third person because of pandemic containment or other force majeure,

the study site's pharmacy may ship the study drug to the home of the subject following approval by the sponsor.

For such a shipment, the following conditions must be met:

- The sponsor is responsible for delivery of the study drug to the study site. Any shipments made from the site to the subject will be the responsibility of the study site.
- The subject is informed about the shipment method, confirms the address for receipt of the drug, and agrees that his or her personal information (ie, name and address) may be given to a professional carrier.
- The pharmacy securely packages the drug for shipment.
- A professional carrier is used by the pharmacy to ship the drug securely and maintain chain of custody, with evidence provided. Acalabrutinib must be stored and shipped at room temperature (15°C to 30°C). The professional carrier must ensure that temperature monitoring is conducted for all shipments.
- To respect subject confidentiality, the carrier should only be given the name and address of the subject. The sponsor should not receive any personal information about the subject.
- A procedure is defined with the carrier to confirm the receipt of the drug by the subject and that it is received in good condition.
- The site contacts the subject to confirm the receipt and integrity of the drug and gives instructions about the drug administration.
- The pharmacy completes its accountability with each shipment made directly to a subject.
